9.1.11 PK Parameters

PK parameters of CVN766 will be derived using non-compartmental analysis methods from the concentration-time data for all evaluable subjects. Actual sampling times, rather than scheduled sampling times, will be used in all computations involving sampling times. The following PK parameters will be determined from concentrations of CVN766 in plasma and CSF:

Symbol/Term	Definition
Plasma	
AUC _t	Area under the plasma concentration-time curve from the time of dosing to the time of the last measurable concentration
AUC _∞	Area under the plasma concentration-time curve from time 0 to infinity, calculated as AUC _∞ =AUC _t +C _{last} /λ _z , where C _{last} is the last quantifiable concentration.
AUC ₂₄	Area under the plasma concentration-time curve from time 0 to 24 hours, calculated using the linear trapezoidal rule.
AUC _τ	Area under the plasma concentration-time curve over the dosing interval (τ)
C _{max}	Maximum observed plasma concentration.
C _{min}	Minimum observed plasma concentration; pre dose trough concentration
CL/F	Apparent clearance after extravascular administration, calculated as Dose/AUC _∞ after a single dose.
CL/F _{ss}	Apparent clearance after extravascular administration at steady state, calculated as Dose/AUC _{tau}
λ _z	Terminal elimination rate constant, calculated as the negative of the slope of the log-linear regression of the natural logarithm concentration-time curve during the terminal phase
t _{1/2z}	Terminal elimination half-life, calculated as ln(2)/λ _z .
t _{max}	Time to reach C _{max} .
V _z /F	Apparent volume of distribution during the terminal phase after extravascular administration, calculated as (CL/F)/λ _z .
V _z /F _{ss}	Apparent volume of distribution during the terminal phase after extravascular administration at a steady-state, calculated as (CL/F _{ss})/λ _z
CSF	
plasma: CSF ratio	ratio of the drug concentration in plasma vs. CSF

Additional PK parameters may be calculated as appropriate.

9.1.12 Procedures for Clinical Laboratory Samples

All samples will be collected in accordance with acceptable laboratory procedures on the days/times stipulated in the Schedule of Study Procedures ([Appendix A](#)).

Table 1 lists the tests that will be obtained for each laboratory specimen.

Table 10 Clinical Laboratory Tests

Hematology	Serum Chemistry	Urinalysis	Special
RBC	ALT	pH	Prolactin

WBC with differential (% and absolute)	Albumin	Specific gravity	TSH
Hemoglobin	Alkaline phosphatase	Protein	(and if abnormal)
Hematocrit	Lipase (d)	Glucose	reflex FT4
Platelets	AST	Blood	
PT/INR	Total bilirubin	Nitrite	
	Direct bilirubin	Microscopic Analysis	
	Total protein	(only if positive dipstick	
	Creatinine	results):	
	Blood urea nitrogen	RBC/high power field	
	Creatine kinase	WBC/high power field	
	GGT	Epithelial cells, casts	
	Potassium	etc.	
	Sodium		
	Glucose		
	Chloride		
	Bicarbonate		
	Calcium		

Diagnostic Screening:

Serum	Urine/ Blood
Serum hCG (a)	Drug screen including amphetamines (AMP), barbiturates (BAR), benzodiazepines (BZO), cannabinoids, cocaine (COC), opiates (OPI), alcohol, cotinine © methamphetamines, methadone (MET), methylenedioxymethamphetamine (MDMA), phencyclidine (PCP), tetrahydrocannabinol (THC)
FSH (b)	
Hepatitis panel, including HBsAg and anti-HCV (e)	
Human Immunodeficiency Virus (HIV) antibody	
	Urine Pregnancy Test (a)

FT4= free T4, FSH= follicle-stimulating hormone, GGT=γ-glutamyl transferase, hCG= human chorionic gonadotropin, PT=prothrombin time, RBC=red blood cells, TSH= thyrotropin, WBC=white blood cells.

(a) Serum hCG pregnancy test will be done at Screening,

Urine Pregnancy Test will be done at Check-in (Day -1).

(b) FSH level will be obtained for female subjects at Screening if they are postmenopausal (i.e., last regular menstrual cycle >2 years) and not surgically sterile. The result must be >40 IU/L for the subject to be enrolled.

(c) To be performed at Screening and Inpatient Check-in (Day -1).

(d) To be performed at Day -1 and 24- and 48-hours post-dose.

(e) Screening Visit only

The local laboratory will perform all clinical laboratory tests. The results of laboratory tests will be returned to the investigator, who is responsible for reviewing and filing these results. All laboratory safety data will be transferred electronically to the sponsor or designee in the format requested by the sponsor. The investigator will maintain a copy of the laboratory accreditation and the reference ranges for the laboratory used.

Laboratory reports must be signed and dated by the Investigator or sub-investigator, indicating that the report has been reviewed and any abnormalities have been assessed for clinical significance. Subjects will be referred to their primary care physician for follow-up of any clinically significant findings or where the investigator or medically trained sub-investigator deems appropriate.

All CS laboratory abnormalities must be recorded as a PTE/AE in the subject’s source documents and on the appropriate eCRF. A CS laboratory abnormality that has been verified by retesting will

be followed until the abnormality returns to an acceptable level or a satisfactory explanation has been obtained.

If subjects experience ALT or AST $>3 \times$ ULN, follow-up laboratory tests at a minimum, serum alkaline phosphatase, ALT, AST, total bilirubin, GGT, and INR should be performed within a maximum of 7 days and preferably within 48 to 72 hours after the abnormality was found.

(Please refer to Section 7.5 for discontinuation criteria and Section 9.8.3 for the appropriate guidance on Reporting of Abnormal LFT in relation to ALT or AST $>3 \times$ ULN in conjunction with total bilirubin $>2 \times$ ULN).

If the ALT or AST remains elevated $>3 \times$ ULN on these 2 consecutive occasions, the investigator must contact the Medical Monitor for consideration of additional testing, close monitoring, possible discontinuation of study medication, discussion of the relevant subject details and possible alternative etiologies. The abnormality should be recorded as an AE (please refer to Section 9.8.3 Reporting of Abnormal LFT for reporting requirements).

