9.1.12 Procedures for Clinical Laboratory Samples

All samples will be collected in accordance with acceptable laboratory procedures on the days/times stipulated in the Schedule of Study Procedures ([Appendix A](#)).

Table 6 lists the tests that will be obtained for each laboratory specimen.

Table 10 Clinical Laboratory Tests

Hematology	Serum Chemistry	Urinalysis	Special
RBC	ALT	pH	Prolactin
WBC with differential (% and absolute)	Albumin	Specific gravity	TSH
Hemoglobin	Alkaline phosphatase (d)	Protein	(and if abnormal) reflex FT4
Hematocrit	Lipase	Glucose	
Platelets	AST	Blood	
PT/INR	Total bilirubin	Nitrite	
	Direct bilirubin	Microscopic Analysis (only if positive dipstick results):	
	Total protein	RBC/high power field	
	Creatinine	WBC/high power field	
	Blood urea nitrogen	Epithelial cells, casts etc.	
	Creatine kinase		
	GGT		
	Potassium		
	Sodium		
	Glucose		
	Chloride		
	Bicarbonate		
	Calcium		
Diagnostic Screening:			

Serum	Urine/ Blood
Serum hCG (a)	Drug screen including amphetamines (AMP), barbiturates (BAR), benzodiazepines (BZO), cannabinoids, cocaine (COC), opiates (OPI), alcohol, cotinine © methamphetamines, methadone (MET), methylenedioxymethamphetamine (MDMA), phencyclidine (PCP), tetrahydrocannabinol (TCH)
FSH (b)	
Hepatitis panel, including HBsAg and anti-HCV (e)	
Human Immunodeficiency Virus (HIV) antibody	

FT4= free T4, FSH= follicle-stimulating hormone, GGT= γ -glutamyl transferase, hCG= human chorionic gonadotropin, PT=prothrombin time, RBC=red blood cells, TSH= thyrotropin, WBC=white blood cells.
 (a) Serum hCG pregnancy test will be done at Screening, Check-in (Day -1), and Inpatient Discharge or Early Termination and at the Follow-up Visit if the subject is brought back to the clinic for re-evaluation.
 (b) FSH level will be obtained for female subjects at Screening if they are postmenopausal (i.e., last regular menstrual cycle >2 years) and not surgically sterile. The result must be >40 IU/L for the subject to be enrolled.
 (c) To be performed at Screening and Inpatient Check-in (Day -1).
 (d) To be performed at Day -1 and 24- and 48-hours post-dose.
 (e) Screening Visit only

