10. Male subjects who do not agree to all the following rules: when sexually active with a female partner(s) of childbearing potential during the study, and for 90 days after the last dose of study drug: a) must use two acceptable methods of birth control (condom or surgical sterilization combined with highly effective method of contraception for the female partner) and b) refrain from sexual activity with female partners who do not use an acceptable method of birth control. Barrier contraception (condom) must be used by all-male subjects who were not surgically sterilized at least 90 days prior to screening. Male subjects must also agree to refrain from sperm donation during the study and until 90 days after the last dose of the study drug.
11. Female subjects who are pregnant or breastfeeding or plan to become pregnant or donate ova during the study or 30 days after the last dose of the study drug. Women of childbearing potential must agree to practice an acceptable method of birth control (e.g., , intrauterine device, barrier, abstinence).

Note: Hormonal contraceptives are not permitted as referenced in Table 3.

*Definitions and acceptable methods of contraception are defined in Section 9.1.13. Contraception and Pregnancy Avoidance Procedure and reporting responsibilities are defined in Section 9.1.14 Pregnancy.

--

12. Subject has previously had a seizure or convulsion (lifetime, with the exception of febrile seizures), including absence seizure.
13. Subject has current or recent (within 6 months) gastrointestinal disease that would be expected to influence the absorption of drugs (i.e., a history of malabsorption, any surgical intervention known to impact absorption [e.g., bariatric surgery or bowel resection], esophageal reflux, peptic ulcer disease, erosive esophagitis, or frequent [i.e., more than once per week] occurrence of heartburn).
14. Subject has a history of cancer or other malignancy, except for basal cell carcinoma or squamous cell carcinoma that has been in remission for at least 3 years prior to Day 1.

15. Subject has a positive test result for hepatitis B surface antigen (HBsAg), hepatitis C virus (HCV) antibody, or a human immunodeficiency virus infection at Screening.

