7.4 Diet, Fluid, Activity Control

Subjects will be confined to the clinic for each of the dosing days as well as a period of time sufficient to collect additional post-dose PK samples and monitor for safety and tolerability (Day -1 through Day 4 for single-dose cohorts and Day-1 through Day 9 for multiple-dose cohorts). During confinement, subjects will be provided 3 standard meals and a snack per day, each containing approximately 30% fat (relative to the total calories). The meals served on the day of dosing should be similar in nutritional content for each subject in the study. The study menu should be recorded and submitted to the study file with a copy provided to the sponsor prior to the start of the study. Breakfast will not be provided on dosing days until at least 1 hour after dose administration unless otherwise indicated (i.e., Days 2-6 for MAD cohorts). The meal start and stop times and percentage of the meal consumed will be recorded in the source and appropriate electronic case report form (eCRF) for all meals served on dosing days.

If a blood draw or any study procedure coincides with a meal, the blood draw will take precedence, followed by the study procedure and then the meal.

Subjects will remain in bed at a semi-supine position for 4 hours following the dose administration, except as necessitated by the occurrence of an AE or study procedures (e.g., obtaining a 12-lead ECG). Subjects must refrain from strenuous exercise from 72 hours before Inpatient Check-in and until check-out.

On the dosing days where extensive PK and/or CSF sampling is indicated (i.e., single-dosing Day 1 and first and last multiple-dose days, e.g., days 1 and 7), CVN766 or placebo suspension will be administered with approximately 240 mL of water after a fast of at least 10 hours. Subjects will continue to fast for an additional 4 hours after dosing and eat lunch following the 4-hour PK blood and CSF collection. Subjects may consume water ad libitum except for 1 hour before and 1 hour after drug administration.

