Complete abstinence, defined as the complete avoidance of heterosexual intercourse - is an acceptable form of contraception if used consistently throughout the duration of study and for the durations after dosing specified for males and females above. It is not necessary to use any other method of contraception when complete abstinence is elected. Females of childbearing potential who choose complete abstinence must continue to have pregnancy tests as per protocol. The reliability of sexual abstinence needs to be evaluated by the Investigator in relation to the duration of the clinical trial and the preferred and usual lifestyle of the subject.

Subjects will be provided with information on acceptable methods of contraception as part of the subject's informed consent process and will be asked to sign an ICF stating that they understand the requirements for avoidance of pregnancy, egg donation, and sperm donation during the study.

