9.1.14 Pregnancy

Women who are pregnant or breastfeeding will not be included in this study.

If any subject is found to be pregnant during the study, she should be withdrawn, and any sponsor-supplied drug should be immediately discontinued. In addition, any pregnancies in the partner of a male subject during the study or for 90 days after the last dose should also be recorded following authorization from the subject's partner.

If the pregnancy occurs during administration of active study medication, e.g., after Visit 1 or within 30 days of the last dose of active study medication, the pregnancy should be reported immediately, using a pregnancy notification form, to the contact listed in Section 1.0.

Should the pregnancy occur during or after administration of the blinded drug, the investigator must inform the subject of their right to receive treatment information. If the subject chooses to receive unblinded treatment information, the individual blind should be broken by the investigator. Subjects randomized to placebo need not be followed.

If the female subject and/or female partner of a male subject agrees to the primary care physician being informed, the investigator should notify the primary care physician that the subject/female partner of the subject was participating in a clinical study at the time she became pregnant and provide details of treatment the subject received (blinded or unblinded, as applicable).

All reported pregnancies will be followed up to the final outcome using the pregnancy form. The outcome, including any premature termination, must be reported to the sponsor. An evaluation after the birth of the child will also be conducted for 8 weeks.

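### The second protocol text schedules no pregnancy test after the last dose or at Early Termination in any of the 8 planned cohorts: a minor safety-schedule gap with a cheap fix

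*Protocol*

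**What the plan says.** This point concerns the second of the two full protocol texts in the file.

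- **Schedule.** Section 9.1.12, Table 10 note (a), gives serum hCG at Screening only, then "Urine Pregnancy Test will be done at Check-in (Day -1". The pregnancy-test rows of the Appendix A grids match, with one extra urine test at Day -1 of the S3 fed period. They are blank at discharge, the outpatient visits, Early Termination and Follow-up. Grid note (f) defines the clinical laboratory row as hematology, chemistry and urinalysis, plus lipase, and hormones in the multiple-dose cohorts. It adds no hCG.
- **Contraception.** Section 7.2, criterion 11, carries the statement "Note: Hormonal contraceptives are not permitted as referenced in Table 3". Section 9.1.13 requires two methods until 30 days after the last dose, or complete abstinence alone, and adds: "Females of childbearing potential who choose complete abstinence must continue to have pregnancy tests as per protocol".
- **Pregnancy.** Section 9.1.14 says "If any subject is found to be pregnant during the study, she should be withdrawn". It asks for reporting when a pregnancy occurs during dosing or "within 30 days of the last dose of active study medication, the pregnancy should be reported immediately", and then: "All reported pregnancies will be followed up to the final outcome using the pregnancy form".
- **Confinement.** Section 7.4 gives "Day -1 through Day 4 for single-dose cohorts and Day-1 through Day 9 for multiple-dose cohorts".

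The other text's note (a) reads "Serum hCG pregnancy test will be done at Screening, Check-in (Day -1), and Inpatient Discharge or Early Termination and at the Follow-up Visit", the last of these applying only if the subject is brought back to the clinic.

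**The concern.** Sections 9.1.13 and 9.1.14 assume that pregnancies in exposed women will come to light, but outside S3 nothing scheduled after Day -1 could reveal one. A woman who conceives shortly before check-in can test negative on Day -1 and then receive a first-in-human drug. What is at stake is the safety follow-up of that pregnancy and, if multiple dosing is extended, the chance to stop before more doses are given. The trial's estimates are not at stake.

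**Working it through.** The protocol states no figure to reproduce. The check is a count of scheduled tests, followed by a rough gauge of what an added test could find.

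**Count, second text, women who complete the study** (note (a) and Appendix A):

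| Cohorts | Scheduled tests | Total | After last dose | At Early Termination |
|---|---|---|---|---|
| S1, S2, S4, S5 | Screening, Day -1 | 2 | 0 | 0 |
| S3 | Screening, Day -1, fed Day -1 | 3 | 0 | 0 |
| M1, M2, M3 | Screening, Day -1 | 2 | 0 | 0 |

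Cohorts with a test after the last dose: 0 of 8. With a test at Early Termination: 0 of 8. With no test after first exposure: 4 + 3 = 7 of 8. In S3 the fed Day -1 test falls at least 14 days after the first check-in, but before that cohort's last dose.

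**The other text, for comparison.** Its grids mark two tests after the last dose in every cohort: Day 4 and Day 8 for S1, S2, S4 and S5; fed Day 4 and 4 days after discharge for S3; Day 9 and Day 14 for the multiple-dose cohorts. Its own note (a) fixes only one (discharge or Early Termination). Its single-dose and S3 grids mark no Day -1 test, although its note (a) names Check-in. The second text marks Day -1 in every grid.

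**What an added test could find.** Assumption, not from the documents: a urine test misses conceptions in the preceding B days, with B between 7 and 14, and conceptions are evenly spread over that period. The share of conceptions missed at check-in that a test I days later finds is min(1, I/B).

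- Single-dose Day 8, S3 fed 4 days after discharge, or before dose 8: I = 1 + 7 = 8. B = 7 gives 100%; B = 14 gives 8/14 = 57%, namely conceptions 6 to 14 days before check-in.
- Multiple-dose Day 14: I = 1 + 13 = 14, giving 100% for B up to 14.
- With the visit one day early and B = 14: single-dose 7/14 = 50%; multiple-dose 13/14 = 93%.

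**What it could not find.** The added test falls 8 - 4 = 4 days (single-dose) or 14 - 9 = 5 days (multiple-dose) after discharge, or 5 and 6 with a one-day-late visit. All are below 7, so it finds no conception after discharge. Of the 30 reporting days, 30 - 3 = 27 (single-dose) or 30 - 2 = 28 (multiple-dose) fall after discharge and still rest largely on self-report.

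**The case against.** The second text is consistent with itself: note (a) and all three grids agree. A reader might infer that Section 9.1.13 is breached because it speaks of continuing tests. It is not, since tests as per protocol are whatever the protocol schedules. Section 9.1.14 sets duties to withdraw, report and follow, not a duty to detect.

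A reader might also infer that two tests were lost by mistake. The documents do not show that. If the second text is current, the other is superseded and a difference from it is no error. Against the other text's own note (a) the contrast is 0 versus 1 fixed test. The second text also marks Day -1 urine tests where the other text's single-dose and S3 grids mark none, and only a test before dosing can prevent exposure.

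The risk is small. Two contraceptive methods or abstinence are required, two tests precede dosing, and subjects are confined through Day 4 or Day 9. Subjects are asked about adverse events at each visit (Section 9.8.1.2) and contacted about 14 days after the last dose (Section 9.3.5). Serum from Day -1 and Day 2 is stored in all cohorts except S3 fed (Section 9.4), so a pregnancy reported later could be dated against exposure.

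All of this stands, and it makes the point minor. It does not remove it: stored serum and general questions trigger no detection, and the fix uses visits that already exist.

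**Conclusion.** The gap is real and worth closing, but minor. In the second text, no planned cohort has a pregnancy test after the last dose or at Early Termination, and 7 of 8 have none after first exposure. The number of pregnancies affected is probably very small and cannot be computed, because the number of women of childbearing potential is not stated. The 57% to 100% shares rest wholly on the assumed 7 to 14 day blind period and are shares of that small number.

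It would go too far to say that later testing protects against exposure in general. It cannot undo a single dose or the planned 7 doses; it finds exposed pregnancies for follow-up. Only a test before dose 8 in an extended cohort could prevent further exposure. No endpoint or analysis changes.

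The finding assumes that the second text governs. This is inferred, since the title pages are not available. The second text does correct slips in the other, such as single-dose discharge at 48 rather than 72 hours in Section 9.3.3. If the other text governs, the finding lapses.

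**What to change.** For women of childbearing potential, amend Table 10 note (a) and the three Appendix A grids to add a urine pregnancy test:

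- at the existing outpatient visit: Day 8 in the single-dose cohorts, 4 days after discharge in S3 fed, and 7 days after the last dose in the multiple-dose cohorts;
- at Early Termination;
- before dose 8, if multiple dosing is extended beyond Day 7.

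The cost is one dipstick per woman: up to 64 in the planned cohorts, or 64 + 24 = 88 if all three planned multiple-dose cohorts are extended. It is fewer in practice because men are enrolled, and more if the Safety Review Group adds cohorts. Urinalysis is already scheduled at single-dose Day 8 and Early Termination. A spot urine may be needed at multiple-dose Day 14, where note (f) names only hormone tests, and before dose 8, where note (f) and the grid's model column for extra dosing days disagree on whether laboratory samples are taken. An occasional false positive will need a confirmatory serum hCG. No visit or invasive procedure is added.

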9.1.13 Contraception and Pregnancy Avoidance Procedure

From the date of signing of ICF, throughout the duration of the study, and for 30 days after the last dose of study medication, females of childbearing potential* must use **two** acceptable methods of contraception and must agree not to donate eggs; Nonsterilized** male subjects who are sexually active with a female partner of childbearing potential* must use **two** acceptable method(s) of contraception throughout the duration of the study, and for 90 days after the last dose of study medication. In addition, males must be advised not to donate sperm for 90 days after the last dose of study medication.

Females of childbearing potential are defined as any female who has experienced menarche and who has not undergone surgical sterilization (hysterectomy or bilateral oophorectomy) and is not postmenopausal.

Menopause is defined as at least 2 years since last regular menses with an FSH >40 IU/L or at least 5 years since last regular menses, confirmed before any study medication is implemented. Male subjects with potentially postmenopausal partners who are under the age of 55 years must use condoms unless their partner's postmenopausal status has been confirmed by FSH level.

**Sterilized males should be at least 90 days post-vasectomy and confirm that they have obtained documentation of the absence of sperm in the ejaculate.

Acceptable and highly effective methods of contraception are:

Note: hormonal contraceptives are not permitted as referenced in Table 3.

- Nonhormonal intrauterine device (IUD)
- Bilateral tubal occlusion
- Vasectomised subject/partner with documented azoospermia 90 days after procedure, if that partner is the sole sexual partner
- Same-sex intercourse, if used consistently for the duration of the study and post dosing as specified above

Complete abstinence, defined as the complete avoidance of heterosexual intercourse - is an acceptable form of contraception if used consistently throughout the duration of study and for the durations after dosing specified for males and females above. It is not necessary to use any other method of contraception when complete abstinence is elected. Females of childbearing potential who choose complete abstinence must continue to have pregnancy tests as per protocol. The reliability of sexual abstinence needs to be evaluated by the Investigator in relation to the duration of the clinical trial and the preferred and usual lifestyle of the subject.

Subjects will be provided with information on acceptable methods of contraception as part of the subject's informed consent process and will be asked to sign an ICF stating that they understand the requirements for avoidance of pregnancy, egg donation, and sperm donation during the study.

